The findings outlined above demonstrate that MDD subjects display blunted reinforcement learning and reduced striatal activation (assessed by fMRI) in response to rewards. Based on the US Department of Health and Human Services (2011), over 63,000 children experienced childhood sexual abuse (CSA) in the US in 2010 alone. Early adversity accounts for 25-32% of adult psychiatric illnesses (Green et al 2010), with over 60% of adults meeting criteria for major depressive disorder (MDD) following CSA (Teicher et al 2009). An even larger risk of depression has been found in those who experienced CSA between the ages of 5-14 years. Preclinical research has shown that early adversities lead to a downregulation of mesolimbic dopaminergic (DA) pathways – including reduced DA transporter (DAT) levels – and a sensitization of the mesocorticolimbic system in response to later acute stressors. These data suggest that increased risk for psychopathology following CSA might be mediated by dysfunctions in mesocorticolimbic DA pathways leading to anhedonia and stress sensitization. Conversely, a well-functioning reward system and increased prefrontal cortex activity might be markers of resilience following adversity. The goals of the proposed research are to (1) test precise hypotheses about the role of DA mechanisms in the sequelae of CSA, and (2) identify biomarkers of resilience. Moreover, to gather a better understanding of the cellular mechanisms linked to these important outcomes, we will use in a small sub-set of the participants (n=20) directed conversion of participants' skin fibroblasts into functional DA neurons to investigate (1) DAT functions in human-induced neuronal cells, and (2) relationships between DAT function and fMRI, PET, and behavioral markers of anhedonia.

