Specific Aim 1: To investigate that increased DA transmission normalizes reward responsiveness and optimism in females with histories of CSA. We will use reward paradigms from our pilot work in conjunction with a pharmacological challenge to test that decreased phasic DA transmission within mesolimbic regions plays a key role in CSA sequelae. We hypothesize that increased phasic DA release – achieved through presynaptic DA autoreceptor blocking by means of single low dose of the D₂/D₃ antagonist amisulpride – will improve positive reinforcement learning and boost activation in reward-related brain regions, particularly the ventral and dorsal striatum (**Hypothesis 1a**). Due to hypothesized downregulation of mesolimbic DA pathways, we expect that individuals with CSA and current MDD (“CSA/MDD”) will show the largest improvements. Confirming that a well-functioning reward system is a marker of resilience, adults with CSA without lifetime psychopathology (“CSA/RES”) will show normative activation and performance under placebo (**Hypothesis 1b**). We also hypothesize that increased phasic DA release – achieved through amisulpride – will re-orient MDD individuals from a pessimistic outlook to an optimistic outlook as measured by the Optimism Bias Task (**Hypothesis 1c**). In addition, under placebo, MDD participants will show a pessimistic outlook as compared with healthy controls (**Hypothesis 1d**).

Specific Aim 2: To investigate dopamine transporter and its relation to reward processing in females with CSA history. We will utilize positron emission tomography (PET) and a highly selective radioactive ligand (¹¹C-altropane) to assess DAT binding in CSA adults. Animal studies have shown that early adversity leads to DAT downregulation within mesolimbic regions. In humans, we have observed links between altropane binding and depressive symptoms, the most common CSA sequelae). Based on our data, we expect that, relative to control and CSA/RES subjects, CSA/MDD adults will show reduced altropane binding (**Hypothesis 2a**). We further hypothesize that, among the CSA/MDD group, reduced DAT will correlate with blunted reinforcement learning and striatal activation (**Hypothesis 2b**).

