Specific Aim 3: To investigate stress sensitization of the mesocortical system following CSA. We will use high-density, source localized electrophysiology (EEG), and cortisol assessments to probe cortical activation and stress reactivity during a reward learning paradigm performed under acute stress. Relative to control and CSA/RES subjects, the CSA/MDD group will show decreased ventromedial prefrontal cortex (vmPFC) activation and increased cortisol reactivity following acute stress accompanied by impaired reward learning (**Hypothesis 3a**). Relative to healthy controls, the CSA/RES

group will show increased vmPFC activation but similar reward sensitivity and cortisol reactivity (**Hypothesis 3b**).

Specific Aim 4a: To investigate DAT function from DA neurons derived from directed conversion of skin fibroblasts. We will collect a skin biopsy from a subset of the study sample (20 participants) to analyze human-induced neuronal DA cells. We hypothesize that relative to the healthy group (n = 8), individuals with MDD and a history of CSA (n=8) will show altered/downregulated DA-related phenotype (e.g., DAT downregulation; **Hypothesis 4a**). **Similarly, we hypothesize that the CSA/RES subjects (n=4) will show similar DA-related phenotype as the healthy group.**

Specific Aim 4b: To Investigate relations between DAT function and fMRI, PET, ERP, endocrinological and behavioral markers of anhedonic behavior and stress responsiveness. Across all groups, downregulated DAT function will be associated with decreased ¹¹C altropane binding in striatal regions (PET), lower reward-related striatal responsiveness (fMRI), potentiated stress-induced cortisol responses, and stress-induced anhedonia (**Hypothesis 4b**).

Specific Aim 4c: To provide more conclusive tests of the potential role of DAT and NOC dysfunction in the pathophysiology of depression. Post-mortem tissue will be obtained from the Douglas Bell Canada Brain Bank in Montreal, QC, Canada through our collaborator [name], Professor and Chair, Department of Psychiatry, McGill University. Please see Appendix 2 for more details.

III. SUBJECT SELECTION

Inclusion Criteria:

- Females of all ethnic origins, age between 20 and 45; right-handed (Chapman & Chapman 1987);
- Absence of any psychotropic medications for at least 2 weeks (6 weeks for fluoxetine; 6 months for neuroleptics; 2 weeks for benzodiazepines; 2 weeks for any other antidepressants);

Childhood Sexual Abuse/MDD (CSA/MDD):

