- At least one incident of contact sexual abuse between the ages 5-14 years;
- Current DSM-IV diagnostic criteria for MDD (as diagnosed with the use of the SCID);

Childhood Sexual Abuse/Resilient (CSA/RES):

- At least one incident of contact sexual abuse between the ages 5-14 years;
- Absence of past or current DSM diagnosis, including MDD or alcohol/substance abuse;

Non-traumatized, MDD (MDD):

- No incidents of childhood sexual, verbal, or physical abuse (ascertained using the Traumatic Antecedents Questionnaire);
- Current DSM-IV diagnostic criteria for MDD (as diagnosed with the use of SCID);

Non-traumatized, healthy controls (controls):

- No incidents of childhood sexual, verbal, or physical abuse (ascertained using the Traumatic Antecedents Questionnaire);
- Absence of any medical, neurological, and psychiatric illness (including alcohol/substance abuse)

Exclusion Criteria:

- Participants with suicidal ideation where study participation is deemed unsafe by the study clinician;
- Women who are not fully fluent (reading, speaking, & writing) in English;
- Pregnant women or women of childbearing potential who are not compliant with the requirements of a urine and blood pregnancy test. Pregnancy is determined by serum pregnancy tests conducted during sessions 1 and 4 and by a urine pregnancy test conducted during session 3.

- Women of childbearing potential not using adequate form of contraception. Adequate contraception includes birth control pills, birth control patch, birth control sponge, birth control vaginal ring, birth control shots, a non-metallic, MRI-compatible intrauterine device (IUD), condom, diaphragm, female condom, spermicide, partner with vasectomy, and abstinence. Those not of childbearing potential include post-menopausal for more than 6 months or surgically sterilized
- Failure to meet MRI or PET safety requirements.
- Serious or unstable medical illness, including cardiovascular, hepatic, renal, respiratory, endocrine (hypothyroidism), neurologic or hematologic disease;
- Past/current DSM diagnosis of: OCD, ADHD, schizophrenia, schizoaffective disorder, delusional disorder, bipolar disorder, mood congruent/incongruent psychotic features, substance dependence, substance abuse within the last 12 months (with the exception of cocaine or stimulant abuse, which will lead to automatic exclusion); Bulimia and Binge Eating Disorder within the last 2 years; Anorexia

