
concentrations of electrolytes, BUN, SGOT, SGPT, CPK, alkaline phosphatase, total bilirubin, albumin, total protein, blood pregnancy test, TSH, eGFR, and electrocardiogram (EKG), and a urine drug test. These tests must be performed within four weeks prior to amisulpride administration.

Preliminary screening for sex, handedness, neurological disorders, exclusionary physical conditions, medication status, weight, history of childhood trauma and history of depression, and MRI and PET safety will take place at the time of the initial telephone contact or interview or via the online screening survey on RedCap (a Partners secure website). Subjects will be re-screened for MRI safety at the beginning of the fMRI session.

To avoid the confounding effects of medication, only subjects off medication will be considered. Importantly, no subject will be requested to discontinue treatment for the purpose of participating in the studies proposed here. Further, if any subject becomes emergently ill or suicidal, access to emergency clinical care will be provided according to established procedures at McLean Hospital. If at any point between signing of consent and the conclusion of the second session, a subject becomes suicidal, homicidal, manic, or psychotic, (s)he will be withdrawn from the study and appropriate care and resources will be provided. Depending on the outcome of the first session, eligible participants will be assigned to one of four groups: (1) CSA between the ages of 5-14 with current diagnosis of MDD (*CSA/MDD*), (2) CSA between the ages of 5-14 without current or past diagnosis of Axis I or II disorders (*CSA/RES*), (3) current diagnosis of MDD without a history of CSA (*MDD*), and (4) healthy controls. Each group will contain 23 subjects who complete at least two imaging sessions (n=23/group).

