Images will be acquired in 3-D mode and reconstructed using a filtered back projection method while modeling the point spread function of the HR+ in the projector to ensure recovery of in-plane spatial resolution of ~ 4.5 mm without increasing noise levels. All projection data will be corrected for nonuniformity of detector response, dead time, random coincidences, and scattered radiation. After realignment, motion-corrected PET frames will be summed, registered to the respective MRI (Woods et al 1993), and transformed into stereotaxic space (Talairach & Tournoux 1988) based on an automated feature-matching algorithm (Collins et al 1994). ROIs will be manually drawn on high-resolution MRI images for dorsal (caudate, putamen) and ventral (NAc) striatal regions. The cerebellum will be used as reference tissue. A simplified reference tissue method (Gunn et al 2001; Lammertsma & Hume 1996) will be used to calculate binding potential. To increase statistical power, a Bayesian method recently developed by the MGH team will be used (Alpert et al 2009; Fang et al 2010). Briefly, this method utilizes prior normative data in a cohort of 51 healthy subjects who underwent 60-min ^{11}C -altropane scan. Bayesian estimates yielded a substantial variance reduction in SRTM parameters, making it possible to reduce the sample size needed to achieve a given power level by $\sqrt{2}$. ANOVAs contrasting age-adjusted altropane binding (covariates: smoking & phase of menstrual cycle) across the groups will be performed. Correlational analyses between binding and (1) response bias in the probabilistic reward task, and (2) beta weights in striatal regions during the reward task, will be run.

Skin Fibroblast Analyses

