After a systematic review of studies investigating Amisulpride use in healthy participants, Rosenzweig and colleagues (2002) concluded that “[Amisulpride] exhibits no significant detrimental effects in psychometric or memory tests up to the dose of 400 mg a day, inducing only mild impairment at high doses, whereas EEG data suggest an alertness enhancing effect at low doses (< 50 mg)” (p. 1). Fifty mg doses have been shown to be without clinically significant detrimental effects in a wide range of psychometric tests intended to explore attention, vigilance, sensory motor coordination and information processing. Single, 100 mg and 200mg doses were also free of deleterious effects on psychomotor performance and body sway. Finally, a single administration of a high dose (400mg) did not cause any alteration in selective and divided attention, motor activity, sensory-motor coordination or vigilance in healthy volunteers. Based on their review, the authors concluded that “In most studies, Amisulpride did not show any sedative effects at dosages up to 400 mg/day in young subjects, or after a single 200 mg dose in elderly subjects” (p. 9).

Hamon-Vilcot and colleagues (1998) administered a single dose of 50 mg Amisulpride to healthy volunteers aged 65-79. Despite the fact that older people are especially sensitive to antipsychotics and many will experience extrapyramidal and anticholinergic effects, “no serious adverse events were recorded” (p. 407). One subject vomited 9 h after dosing. A further subject complained of mild somnolence lasting 12 h, which occurred 4 hrs after dosing. No extrapyramidal symptoms were observed. Neither clinically significant hemodynamic variations nor ECG abnormalities were observed during the study. Overall, these findings indicate that a single dose of 50 mg Amisulpride was not associated with any clinically significant side effects. Importantly, to minimize age-related fluctuations in dopamine levels, our protocol proposes to include only participants between the age of 20 and 45. Accordingly, the likelihood that sedation or nausea will occur will be further diminished.

Samuels and colleagues (2006) administered to 16 healthy males a 50-mg Amisulpride dose, and its functional effects were assessed at peak plasma levels. The following side effects were recorded.

- | | |
|---|--------|
| o Sleepiness (3 mild, 1 moderate, 2 severe= 6 total) | 37.50% |
| o Nausea (2 mild) | 12.50% |
| o Vomiting 0 | 0% |

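### The four groups are neither randomised nor age-matched within 20 to 45, yet age is adjusted for only in the PET analysis and not in the PRT, FRN/source, PSST/MID or fMRI group models

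*Combined protocol and SAP*

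**What the plan says.** **Groups.** Section III sets one age rule for everyone: "Females of all ethnic origins, age between 20 and 45; right-handed". CSA/RES is described three times in consistent terms: "adults with CSA without lifetime psychopathology" (Section II.a, Aim 1), "Absence of past or current DSM diagnosis, including MDD or alcohol/substance abuse" (Section III), and "without current or past diagnosis of Axis I or II disorders" (Section IV.a, where groups are assigned on the outcome of the first session). No diagnostic follow-up is planned. CSA/MDD requires a current MDD diagnosis.

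**Matching.** Among the four study groups, the only matching is of CSA/MDD with MDD on comorbidities (Section III, exclusion criteria). Demographic matching is mentioned only for the post-mortem tissue (Section V.a and Appendix 2), which lies outside the four-group comparison.

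**Age in the plan.** Appendix 1 gives a reason for the age limits: "to minimize age-related fluctuations in dopamine levels, our protocol proposes to include only participants between the age of 20 and 45". Section VI.a, PET Analyses, states: "ANOVAs contrasting age-adjusted altropane binding (covariates: smoking & phase of menstrual cycle) across the groups will be performed". No other analysis in Section VI.a names age. The other adjustments named there are conditional: SRTT performance if groups differ in procedural learning, and brain volume in the fMRI data if applicable.

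**Blind.** Section V.a, Randomization, says that the blind was broken in May 2016 for preliminary analyses. It foresees only a few more participants, to replace unusable data.

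**The concern.** The goal of identifying biomarkers of resilience rests on comparing CSA/RES with CSA/MDD and with controls. These are observational contrasts, even though drug is allocated within each group. The groups are formed by different diagnostic rules, one of which (no diagnosis so far) depends on how long a woman has lived. Equal age distributions therefore cannot be taken for granted.

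The plan already accepts that age matters for dopamine and adjusts for it in one component. The reward-learning, ERP and fMRI components test the same dopamine account without that protection. If the groups differ in age and the outcome varies with age, part of a CSA/RES contrast is an age effect. It could appear as a marker of resilience. It could also hide a real difference, which matters because Hypotheses 1b and 3b partly predict that CSA/RES resembles controls.

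**Working it through.** **1. Age control, component by component (Section VI.a)**

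| Component | Group model in the plan | Age term |
|---|---|---|
| PRT (Hypotheses 3a, 3b) | Group x Block | none |
| FRN | Group x Electrode | none |
| Source analysis | voxelwise tests with permutation | none |
| PSST and MID behaviour (1a, 1b) | Group x Drug x Trial Type | none |
| fMRI regions of interest (1a, 1b) | Group x Condition x Hemisphere x Trial | none |
| PET binding (2a) | ANOVA across groups | yes |

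**2. The plan's own figures.** The plan gives no figure for age. The nearest are the planning effects and power in Section VI.d. The means reproduce: (0.85 + 0.70 + 1.45)/3 = 1.00 for behaviour and (0.78 + 0.87 + 1.80)/3 = 1.15 for fMRI. With 23 v 23 and alpha 0.05, normal-approximation power is 0.960 and 0.988 one-sided, in line with the stated bound of more than 0.95. Two-sided it is 0.924 and 0.974. The plan does not state sidedness. These calculations cover controls v CSA/MDD and drug v placebo within CSA/MDD. No CSA/RES contrast was sized.

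**3. What an unadjusted age gap would do (assumed inputs).** Let r be the within-group correlation of outcome with age and D the age gap between two groups in within-group SDs. The documents give neither, so both are assumptions.

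- Spurious standardised difference = r x D.
- Standard error with n per group, in SD units = sqrt(2/n). For n = 23 this is 0.295.
- With b = r x D / sqrt(2/n), the two-sided false-positive rate at nominal 5% = 1 - Phi(1.96 - b) + Phi(-1.96 - b).

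Hypothesis 1b is tested under placebo, so about 23/2 = 11.5 women per group, with standard error sqrt(2/11.5) = 0.417.

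| r | D | Spurious d | False positives, 23 v 23 | False positives, 11.5 v 11.5 |
|---|---|---|---|---|
| 0.2 | 0.5 | 0.10 | 6% | 6% |
| 0.2 | 1 | 0.20 | 10% | 8% |
| 0.5 | 0.5 | 0.25 | 14% | 9% |
| 0.5 | 1 | 0.50 | 40% | 22% |

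If D = 0 or r = 0, there is no bias. The sign follows the sign of r x D, which is unknown.

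**4. Which contrasts are exposed.** Half of each group receives amisulpride and half placebo. Within a group, an age main effect with slope beta adds beta x (mean age on drug - mean age on placebo) to the drug effect. With random allocation its expected value is zero whatever the group's mean age. The Group x Drug x Trial Type effect compares these within-group drug effects, so an age main effect does not create it; age would have to modify the drug effect. The exposed contrasts are those across groups: the PRT and FRN/source group effects, the placebo-arm comparisons behind Hypothesis 1b, and the planned comparison of controls on placebo with CSA/MDD on amisulpride.

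**The case against.** The strongest reply is that nothing in the documents shows an age difference. All groups share the 20 to 45 limits, which Appendix 1 presents as a control on age-related dopamine variation. CSA/MDD is defined by a current episode rather than by ever having had one, so there is no evidence that these women are older. Much of this stands: the direction and size of any gap are conjecture, and the table in the working rests on assumed inputs. But a shared 25-year range limits the spread of age without balancing it between groups, and the plan evidently did not think the limits sufficient for PET.

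A reader might go further and infer that CSA/RES contains many women who have not yet passed through the risk period and will later become depressed, pointing to "with over 60% of adults meeting criteria for major depressive disorder (MDD) following CSA". The documents do not support putting a number on that. They give no onset ages and no risk window, and do not call the figure a lifetime risk or give the age at assessment. It also concerns MDD after CSA in general, whereas CSA/RES excludes every past or current diagnosis. Any conversion rate would be set by the assumed onset window.

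Nor does the plan claim that CSA/RES women will stay well. The criteria plainly describe history to date, and Hypotheses 1b and 3b are cross-sectional. What remains is a point of wording: conclusions should not go beyond that definition.

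**Conclusion.** The concern holds as a gap in adjustment. Four non-randomised groups are compared without age matching, and only PET is age-adjusted although the protocol itself links age to dopamine. The between-group contrasts behind Hypotheses 1b, 3a and 3b are open to age bias of unknown size and direction. Under the assumed ranges the spurious difference is 0.10 to 0.50, at most half the behavioural planning effect (0.50/1.00). False-positive rates are then 6% to 40% with 23 per group and 6% to 22% in placebo-only contrasts. These show what the plan leaves possible; they are not estimates for this study.

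Two stronger readings are not supported: that CSA/RES is known to be younger or to contain a calculable share of future cases, and that the Group x Drug x Trial Type effect is biased by an age main effect.

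**What to change.** - Add age (centred) as a covariate to the between-group part of the PRT, FRN/source, PSST/MID and fMRI models, as PET already does. Where a group effect is read from an interaction with a repeated factor, such as Group x Block, include age's interaction with that factor. The source-space permutation tests need a scheme that accepts a nuisance covariate.
- Because preliminary unblinded analyses have been run, declare the change in a dated amendment and show the unadjusted result beside the adjusted one, so that the covariate cannot appear chosen for its effect.
- Report the age distribution by group.
- Word CSA/RES conclusions as no diagnosis to date.

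**Cost.** Age is already needed for eligibility, so no new data are required. With 92 women, the between-subject error degrees of freedom fall from 92 - 4 = 88 to 87 in the Group models and from 92 - 8 = 84 to 83 in the Group x Drug models. Covariate adjustment assumes a roughly linear, common age slope and overlapping ages; the age table lets a reader check the overlap. Age matching at enrolment is not proposed, since only a few participants may remain to be recruited.

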The subjects for this research will be 184 females (20-45 years) recruited from the greater Boston area by McLean Hospital's Center for Depression, Anxiety and Stress Research. Only females will be recruited due to expected sex-specific differences in (i) abuse-related (e.g., child-perpetrator gender) and unrelated variables (e.g., brain development; Pechtel & [name] 2010), and (ii) HPA axis reactivity (e.g., Young & Korszun 2010). No employees of McLean Hospital, or students or employees of Harvard Medical School will be enrolled.

IV. SUBJECT ENROLLMENT

a. Methods of enrollment

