Subjects will be paid \$15/hour for the SCID session (session 1), up to \$70 for the ERP session including \$38 for completing the EEG and up to \$32 on the probabilistic reward task, up to \$150 for the fMRI session including \$100 for completing the session and up to \$50 on the MID task, and \$200 for the PET session. In addition, participants who complete all four sessions of the study will earn an additional \$75. Lastly, if participants complete only part of a study session, they will be compensated in a prorated manner, such that if they complete half of a study session, they will be compensated half of the total amount (e.g., participant completes half of the PET scan session, he/she will be compensated \$100). If the participant completes all of the sessions, they can earn up to \$555. The subset of subjects who participate in the additional skin fibroblast study (n=20) will be compensated \$100.

Randomization

For protocol 2010-P-002593, all subjects in study are administered a single low dose of amisulpride (50 mg) in order to test the role of dopaminergic mechanisms in the pathophysiology of MDD. This proof-of-mechanism study uses a double-blind, placebo-controlled between-subject design (for each group in study, 50% of the subjects in each group will receive placebo, with the remaining 50% receiving a single dose of amisulpride), involves a single MRI session, and does not include a treatment component. Though data collection has not yet been completed, the blind was broken as of May 2016 to conduct preliminary analyses. Accordingly, the medication blind will be broken as of November, 2016 in order to allow further analyses. In order to preserve the scientific integrity of the study, we propose the following precaution:

The Research Assistant responsible for running participants ([name]), the study doctors ([name], [name]), and any other member of the [name] Lab who directly interacts with participants will remain blind to drug group assignment. Accordingly, if we discover during statistical analyses that a few participants yielded unusable data (e.g., due to excessive motion artifacts), we will be able to enroll and test a few final participants in a fully unbiased way.

b. Drugs to be used

Amisulpride

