Comparison of Molecular and Cellular Properties of Converted DA Neurons from Fibroblasts of MDD/CSA (n=8), CSA/RES (n=4), and Psychiatrically Healthy Subjects (n=8): Once we optimize conversion of fibroblasts to mDA neurons, we will use these biopsied fibroblasts to convert them to mDA neurons using our optimized protocol. To evaluate whether converted DA neurons from each group have distinct properties, we will test their ability to synthesize and release DA in response to membrane depolarization. We will treat *in vitro* differentiated cells with 50 mM KCl for 30 minutes and assess DA release by HPLC. Media will be collected after 30 min then concentrated perchloric acid (PCA) will be added to a final concentration of 0.1 M PCA/0.1mM EDTA. The DA content of the supernatants will be measured by reverse-phase HPLC. We will also compare mRNA expression patterns for dopamine-related genes such as synthesizing (TH and AADC), uptake (DAT), degrading (MAO and COMT), and storage function (VMAT2) at mRNA and protein levels in converted mDA neurons of each group.

Plasma Samples

Concentrations of pro- and anti-inflammatory cytokines and related receptors will be assessed using enzyme-linked immunosorbent assays (ELISA, R&D systems, Minneapolis, MN). All assays will be performed at the CLIA-certified Harvard Catalyst Central Laboratory (HCCL) in accordance with manufacturer specifications, and will be run in duplicate.

b. Study endpoints

Not applicable

c. Statistical methods

Please see above.

d. Power analysis

Sample size and power calculations

Sample size was estimated after considering effect sizes obtained in preliminary studies. Effect sizes were calculated using $p = 0.05$ for detecting differences between (1) controls vs. CSA/MDD, and (2) CSA/MDD receiving a DA challenge vs. placebo. Based on these estimates and allowing for 5% data loss, the sample size is 92 (23 subjects/group). In our study using the PSST task proposed, relative to controls, women with histories of CSA and MDD showed lower accuracy in trials in which they needed to rely on reward (Cohen's $d = -0.85$). In a study using the probabilistic reward task, we found that unmedicated MDD subjects had significantly reduced response bias compared to controls ($d = -0.70$; [name] et al 2009b). In another study using the same task, we found that healthy subjects receiving

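### Stated power uses all 92 subjects although 92 already allows for 5% data loss; 184 recruited, 92 sized and 23 completers per group are not reconciled

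*Combined protocol and SAP*

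**What the plan says.** Three sample sizes appear in three places.

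- Section III.b (Source of subjects and recruitment methods): "The subjects for this research will be 184 females (20-45 years"). No split by group or drug is given.
- Section IV.a (Methods of enrollment): "Each group will contain 23 subjects who complete at least two imaging sessions (n=23/group"), which is 4 × 23 = 92 completers.
- Section VI.d (Power analysis): "Based on these estimates and allowing for 5% data loss, the sample size is 92 (23 subjects/group").

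VI.d names two sizing contrasts: controls against CSA/MDD, and CSA/MDD on a dopaminergic challenge against placebo. It then states power above 0.95 for group differences with 92 subjects, at mean effects of 1.00 (behavioural) and 1.15 (fMRI). For PET it states power above 0.85 with 92 subjects, at an expected d above 0.80. No separate power is given for the drug contrast. The Randomization text in Section V.a splits each group equally between amisulpride and placebo.

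**The concern.** If 92 is the number before a 5% loss, it cannot also be the number on which the analyses run. If 23 per group are completers, it is unclear what the 5% refers to. The figure of 184 is exactly twice 92, and nothing in the text says at what stage it is counted.

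VI.d is the only justification of sample size, so a reader judging a null result needs to know how many subjects each comparison was expected to have. This matters most for the drug contrast. It is one of the two contrasts named for sizing, but it uses half of one group on each side, whereas the stated power is for group differences.

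**Working it through.** **Inputs.** From VI.d: 92 subjects, 23 per group, 5% loss, and effects of 1.00, 1.15 and 0.80. The pilot drug-challenge effects there are 1.45 (pramipexole, behavioural) and 1.80 (bupropion, fMRI). The 1:1 drug split within group is from V.a. On alpha, VI.d says only "Effect sizes were calculated using $p = 0.05$ for detecting differences between" the two contrasts. Sidedness is not stated, so both are shown.

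**Formula.** Two-sample t-test with n₁ and n₂ subjects: noncentrality λ = d·√(n₁n₂/(n₁+n₂)), degrees of freedom n₁+n₂−2, power from the noncentral t distribution at 0.05.

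**Reproducing the plan's figures at 23 v 23.** For d = 1.00, λ = √(529/46) = 3.39.

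| d | Stated | Two-sided | One-sided |
|---|---|---|---|
| 1.00 | >0.95 | 0.912 | 0.955 |
| 1.15 | >0.95 | 0.968 | 0.986 |
| 0.80 (PET) | >0.85 | 0.756 | 0.848 (normal approximation 0.857) |

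The stated figures therefore match a comparison of 23 v 23. One-sided, all three are met or nearly met; two-sided, only d = 1.15 is.

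**Can 92 include the 5%?** Yes. At d = 1.15, two-sided power of 0.95 needs 21 per group; 21/0.95 = 22.1, rounded up to 23, and 4 × 23 = 92. Had 92 been required as usable, the inflated number would be 92/0.95 = 96.8, so 97.

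**Analysable number on VI.d's wording.** 92 × 0.95 = 87.4, or 21.9 per group, taken as 22.

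| d | Stated | Two-sided, 22 v 22 | One-sided, 22 v 22 |
|---|---|---|---|
| 1.00 | >0.95 | 0.90 | 0.947 |
| 1.15 | >0.95 | 0.96 | 0.98 |
| 0.80 (PET) | >0.85 | 0.74 | 0.83 |

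The loss itself costs about 1 to 2 points. Most of the two-sided gap for PET comes from sidedness: 0.848 becomes 0.756 at 23 v 23 before any loss. At d = 1.00 the one-sided miss is marginal, since the normal approximation gives Φ(3.317 − 1.645) = Φ(1.672) = 0.953.

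**CSA/MDD drug versus placebo.** Halving 23 gives 11 v 12, and halving 22 gives 11 v 11. For d = 1.00 at 11 v 12, λ = √(132/23) = 2.40.

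| d | 11 v 12, two-sided (one-sided) | 11 v 11, two-sided (one-sided) |
|---|---|---|
| 1.00 | 0.63 (0.75) | 0.61 (0.73) |
| 1.15 | 0.75 (0.85) | 0.73 (0.83) |
| 1.45 | 0.91 (0.96) | 0.90 (0.95) |
| 1.80 | 0.98 (0.99) | 0.98 (0.99) |

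**Where 1.00 and 1.15 come from.** (0.85 + 0.70 + 1.45)/3 = 1.00 and (0.78 + 0.87 + 1.80)/3 = 1.15. Each averages two group differences with one drug effect, so neither describes one contrast.

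**The case against.** The strongest reply is that the figures describe successive stages. Consent, diagnostic interview and laboratory screening all take place in Session 1, and groups are formed only afterwards: "Depending on the outcome of the first session, eligible participants will be assigned to one of four groups". The Randomization text shows what data loss may mean: "if we discover during statistical analyses that a few participants yielded unusable data (e.g., due to excessive motion artifacts"). On that reading 184 are recruited, 92 complete, and about 87 give usable data. This is coherent, and it stands as a possibility. The protocol does not state it, however, and gives no screen-failure rate.

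A reader might infer that the figures contradict each other, or that 92/184 = 50% reveals a dropout rate ten times the 5% allowed. The documents do not support either. The step from 184 to 92 may include subjects who fail Session 1 and never receive the drug, so it is a different quantity from the 5%. A reader might also note that 184 = 8 × 23 and suppose 23 per group-by-drug cell was meant. No passage says so: IV.a and VI.d both give 23 per group, and V.a halves each group. Nor does 184 enter any stated power, which rests on 92 throughout.

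On the drug contrast, a reader might take the >0.95 to cover it. VI.d attaches that figure to group differences only. At the pilot drug effects, power at 11 v 12 is 0.91 or more, so the contrast is not necessarily underpowered. Those effects come from other drugs, and one of them from healthy subjects, so they do not settle the matter.

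**Conclusion.** The point holds as a failure to reconcile the figures and as a power statement made at the wrong number. VI.d treats 92 as loss-inclusive and then computes power as if all 92 were analysed. At about 22 per group the PET claim falls short whichever sidedness is used. The d = 1.00 claim falls clearly short two-sided and marginally one-sided, and the d = 1.15 claim survives. If 92 instead means usable subjects, the loss correction disappears but the 5% sentence is then wrong, and the two-sided shortfalls at d = 0.80 and d = 1.00 remain.

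The larger uncertainty is the named drug contrast, which has no stated power. At 11 v 12 its two-sided power runs from 0.63 to 0.98 across effects that VI.d itself cites. The missing link between 184 and 92 is, taken alone, a matter of wording. These results assume equal groups, a two-sample t-test at 0.05, and loss spread evenly over groups and drug arms.

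**What to change.** 1. In III.b, say what 184 counts (for example, women consented at Session 1) and how it leads to 92.
2. In IV.a and VI.d, say whether 23 per group is before or after the 5% loss, and whether that loss means dropout or unusable data.
3. In VI.d, restate power at the analysable number, with sidedness, separately for the between-group contrast and for drug versus placebo within CSA/MDD. For the latter, give the cell sizes and a range of effects.

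The 5% should not be replaced by 50%: losses between recruitment and group assignment do not belong in that allowance. The cost is a few sentences and a recomputed power paragraph, with no extra patients. Although the blind has already been broken for preliminary analyses, the restated power would still inform how a null drug result is read.
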